5. CHANGES TO PLANNED ANALYSES

Any changes to the analyses from procedures outlined in this SAP will be summarized in the associated interim or final CSR. Decisions to deviate from planned analyses will be documented at the time they are made.

5.1. Changes from Analyses Specified in Study Protocol

Changes from Protocol (Version 13.0) to SAP (Version 3.0) are listed below:

Protocol Section	Section Title	Text in Protocol	Change from Protocol in SAP and Rationale
			No change

5.2. Changes from Previous SAP (Version 2.0)

Section Number	Section	Changes
4.4.1	Analysis of Primary Efficacy Endpoint	
Clarified that only the supplementary analyses for Group C subjects based on the protocol VOEs and the investigator VOEs in TPVOE will be performed for the final CSR.
 
Removed the supplementary analysis in the ITT population with ≥ 4 protocol VOEs in the 24 months prior to Informed Consent. The analysis was performed for the interim CSR, in case the agency wanted the analysis based on the ITT population. The result was however not of the agency's interest. Moreover, this analysis was heavily weighted by subjects who discontinued prior to receiving the benefit of treatment.

4.4.2.1	Adjudicated sVOE-CR	
Clarified that only the supplementary analysis for Group C subjects based on the protocol sVOEs in TPVOE will be performed for the final CSR.
 
Removed the supplementary analysis in the ITT population with ≥ 4 protocol VOEs in the 24 months prior to Informed Consent. See the change above made in Section 4.4.1 for the rationale.

4.4.2.2	Globin Response	Removed the imputation rules of missing HPLC assessments due to COVID-19 pandemic. The imputation rules were never implemented, because of no such cases in data by the end of the pandemic.

Section Number	Section	Changes
		Removed the supplementary analysis in the ITT population with ≥ 4 protocol VOEs in the 24 months prior to Informed Consent. See the change above made in Section 4.4.1 for the rationale.
4.4.3.1	Characterization of Globin Response	Added a supplementary analysis. In the definition, added “After achieving Globin Response, subjects with death or discontinuation unrelated to the drug product will be considered as not evaluable.” This is to exclude the subject who discontinued due to sudden death which was unrelated to the drug product, according to communication with the agency.
4.4.3.2	Hematologic Endpoints	Removed “starting from Month 1 post-drug product infusion”.
4.4.4	Analysis of Exploratory Efficacy Endpoints	Added the analyses of bone marrow smear.
4.4.5	Analysis of Correlation	Added the correlation between HbAT87Q vs. HbS (% of non-transfused total Hb) at Month 6
4.5	Pharmacodynamic Analysis and Correlation Analysis	Deleted the spaghetti plots of PB %LVV+ and AUC of sickled RBCs, and the correlation analyses related to the two parameters.
4.6.1	Adverse Events	Added AE/SAE attributed to SCD post Month 6
4.6.2	Engraftment	Added a supplementary analysis for time to PE. This is to extend the time to PE for subjects who took eltrombopag before achieving PE to align with the label.
4.6.3	Laboratory Data	Added hematology RDW test. Added the analysis of cytopenia.
4.6.7	Persistent Oligoclonality and Integration Site Analysis (ISA)	Updated the algorithm used for ISA to align with Protocol Version 13.0.
6.1	Imputation Rules for Missing Data	Updated the imputation rule for AE end date by replacing data cut-off date with last follow-up date. Updated the imputation rule for missing adjudicated VOE end date.
6.2	Analysis Visit Windows	Added analysis visit window for RDW.
6.7	Search Strategy for Events of Interest	Added thromboembolic events

6. APPENDIX

6.1. Imputation Rules for Missing Data

Table 11. Imputation Rules for Missing Data

Situations	Imputation rules
AE	
Start/onset date is incomplete
If the day of the month is missing, the onset day will be set to the first day of the month unless it is the same month and year as study drug treatment (i.e., drug product infusion). In this case, in order to conservatively report the event as treatment-emergent, the onset date will be assumed to be the date of study drug treatment, except in cases where this will lead to a start date being after stop date. In these situations, the original rule will be applied.If the onset day and month are both missing, the day and month will be assumed to be January 1, unless the event occurred in the same year as the study drug treatment. In this case, the event onset will be coded to the day of study drug treatment to conservatively report the event as treatment-emergent, except in cases where this would lead to a start date being after stop date. In these situations, the original rule will apply.A missing onset date will be coded as the day of study drug treatment, except when this would lead to a start date being after the stop date. In these situations, the start date will be set to the first day of the month of the AE end date.
End date is incomplete	
If the day is missing, it will be set to the last day of the month or the last follow-up date, whichever occurs first.If both the day and the month are missing, it will be set to December 31 or the last follow-up date, whichever occurs first.If the end date is completely missing, it will be set to the last follow-up date
Prior/Concomitant and Non-drug treatment start and end date to support analyses of (s)VOE, VOC/ACS, (s)VOE start and end date	
If the imputed start date is after the stop date, then the imputed start date will be one day prior to the stop date.If the imputed end date is after the end of study date or DCO (data cut-off date), then the imputed date will be set as set to DCO or end of study date, whichever occurs earlier.

Situations	Imputation rules
Start date is missing or partial	
 – if month is missing, use January – if day is missing, use the first day of the month under consideration – if year is missing, use year of the Informed Consent date – if entire date is missing, use Informed Consent date - 1 (not applicable to VOE or sVOE start date)
End date is missing or partial	
 – if month is missing, use December – if day is missing, use the last day of the month under consideration – if year or the entire date is missing, set to DCO or end of study date, whichever occurs earlier – for adjudicated VOE, impute the missing entire VOE end date as below: 
 • If adjudicated VOE start date is on or after conditioning start date, then the imputed date will be set to data cut-off date or end of study date, whichever occurs earlier • If adjudicated VOE start date is before conditioning start date, then the imputed date will be one day prior to the conditioning start date
SCD diagnosis date or Medical History diagnosis date	
(1) Only Day is missing	Set to 01 Month Year or DOB (date of birth), which occurred last
(2) Both Day and Month are missing	Set to 01 January Year or DOB, which occurred last
(3) Completely missing	Set to DOB
Missing age (years) at Diagnosis of SCD	
 – If DOB and SCD diagnosis date are complete, calculate the age = (SCD diagnosis date – DOB)/365.25, and round down to the integer – Otherwise, if at least Month and Year available in DOB and SCD diagnosis date, replacing the missing Day by 01 and calculate the age as the same formula above; if the imputed age is negative, assign it as 0. – If only Year is available in DOB or SCD diagnosis date, the age = Year of SCD diagnosis date – Year of DOB

Situations	Imputation rules
Missing age (years) at starting regular transfusion	
 – If DOB and starting regular transfusion date are complete, imputed the age = (starting regular transfusion date – DOB)/365.25, and round down to the integer – Otherwise, if at least Month and Year available in DOB and starting regular transfusion date, replacing the missing Day by 01 and calculate the age as the same formula above; if the imputed age is negative, assign it as 0. – If only Year is available in DOB or in starting regular transfusion date, the age = Year of starting regular transfusion date – Year of DOB – If starting regular transfusion date is completely missing, the age is missing
Hospital or ER dates (date admitted, or date discharged)	
 ○ If Day is missing: 
 - If the month of discharge is after the month of admission, and day of discharge is missing, then set as 01 for the missing day - If the month of discharge is after the month of admission, and both day of discharge and admission are missing, then set as 01 for the missing day - If the month of discharge is the same the month of admission, then duration of hospital = 1 ○ If both Month and Day are missing in either date, no imputation for duration of hospital. ○ At interim analysis, if a subject has not been discharged from the hospital for drug product infusion, the duration of hospital will be the days between the last follow up date and admission date
Transfusion information	
 ○ If it is known a transfusion took place with number of pRBC unit but pRBC volume (mL) is missing: the standard volume per unit (300 mL) will be substituted ○ If it is known a transfusion took place, but neither number of unit nor volume is reported: 
 - For transfusion recorded before drug product infusion: mean volume that the subject received in the 2 years prior to enrollment will be substituted - For transfusion recorded on or after drug product infusion: 
 a) If there are transfusions on or after drug product infusion and before the record with the missing value, the mean volume that the subject received during this time frame will be substituted. b) If no other transfusions have been given during this time frame, then the mean volume from ICF to pre-study drug will be used. c) If all volumes are reported in units and there is no standard volume per unit provided, then 300 mL/unit will be imputed

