6.2.5. Vaso-occlusive Events (VOEs)

All VOEs 24 months prior to ICF and following ICF for the duration of the study will be recorded. VOE categories include acute pain with no medically determined cause other than VOE (e.g., VOC), acute chest syndrome (ACS), acute hepatic sequestration, acute splenic sequestration, and acute priapism. All VOEs that, in the opinion of the Investigator, represent at least one of these events (regardless of duration, severity, treatment, or need for medical facility visit) must be recorded. A VOE can be home-managed only, and does not require a visit to a medical facility or hospitalization to be reported. It is recognized that retrospective collection of VOE information may be challenging; however, complete collection and reporting of VOEs should be done to the best of the clinical site's ability.

Subject eligibility is determined by the Investigator based on that subject having at least 4 protocol-defined severe VOEs (i.e., protocol sVOEs) in the 24 months prior to ICF as set forth in [Section 4.2](#).

For the purposes of this study, a protocol-defined VOE (i.e., protocol VOE) is any of the following events (with or without hospitalization):

- a. an episode of acute pain with no medically determined cause other than a VOE (e.g., VOC) lasting more than 2 hours and requiring care at a medical facility
- b. ACS, defined by an acute event with pneumonia-like symptoms (e.g., chest pain, fever [$> 38.5^{\circ}\text{C}$], tachypnea, wheezing or cough, or findings upon lung auscultation), and the presence of a new pulmonary infiltrate consistent with ACS, and requiring oxygen treatment and/or blood transfusion
- c. acute hepatic sequestration, defined by a sudden increase in liver size associated with pain in the right upper quadrant, abnormal results of liver-function test not due to biliary tract disease, and reduction in Hb concentration by at least 2 g/dL below the baseline value
- d. acute splenic sequestration, defined as sudden enlargement of the spleen and reduction in Hb concentration by at least 2 g/dL below the baseline value

- e. an event of acute priapism: defined as a sustained, unwanted painful erection lasting more than 2 hours and requiring care at a medical facility

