4.4.1. Analysis of Primary Efficacy Endpoint

Analysis for Group C

The primary efficacy endpoint, VOE-CR, is defined as the complete resolution of adjudicated VOE between 6 months and 18 months after drug product infusion. The analysis population can be found in [Table 4](#).

Responders of VOE-CR are subjects who do not have any adjudicated VOEs between 6 months and 18 months (i.e., 183 to 548 days) after drug product infusion.

Non-Responders of VOE-CR are subjects who meet any of the following criteria:

- Has ≥ 1 adjudicated VOE between 6 months and 18 months after drug product infusion. If a subject has an adjudicated VOE that occurs before 183 days but ends after 183 days after drug product infusion, the subject is considered as a non-responder.
- Discontinues from the study on or before 18 months follow-up post-drug product infusion.

The percentage of subjects who achieve VOE-CR will be presented with a 2-sided exact 95% CI using Clopper-Pearson method for the binomial distribution. The success criterion will be at least 21 out of 35 subjects achieving VOE-CR (i.e., rate of VOE-CR $\geq 60\%$), giving a lower bound of the 95% CI greater than 40%, if exactly 35 TPVOE subjects in Group C. If there are fewer than 35 subjects in the analysis population, with the same assumptions such as the null hypothesis as 40% and alternative hypothesis as 80%, the power and success criterion can be found in [Appendix 6.3, Table 13](#).

Supplementary Analyses for Group C

The following Supplementary analyses, but not limited to, will be conducted:

Analysis Population	Supplementary Analysis
TPVOE ^[1]	The primary analysis will be repeated using protocol VOE instead of adjudicated VOE.
TPVOE ^[1]	The primary analysis will be repeated using investigator VOE instead of adjudicated VOE.

Analysis Population	Supplementary Analysis

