4.4.2. Analysis of Key Secondary Efficacy Endpoints

4.4.2.1. Adjudicated sVOE-CR

Analysis for Group C

One of the key secondary efficacy endpoints, sVOE-CR, is defined as the complete resolution of adjudicated sVOE between 6 months and 18 months after drug product infusion. The analysis population can be found in [Table 4](#).

Responders of sVOE-CR are subjects who do not have any adjudicated sVOEs between 6 months and 18 months (i.e., 183 to 548 days) after drug product infusion.

Non-Responders of sVOE-CR are subjects who meet any of the following criteria:

- Has ≥ 1 adjudicated sVOE between 6 months and 18 months after drug product infusion. If a subject has an adjudicated sVOE that occurs before 183 days but ends after 183 days after drug product infusion, the subject is considered as a non-responder.
- Discontinues from the study on or before 18 months follow-up post-drug product infusion

The percentage of subjects who achieve sVOE-CR will be presented with a 2-sided exact 95% CI using Clopper-Pearson method for the binomial distribution. The success criterion will be at least 24 out of 35 subjects achieving sVOE-CR (i.e., rate of sVOE-CR $\geq 69\%$), giving a lower bound of the 95% CI greater than 50%, if exactly 35 TPVOE subjects in Group C. If there are fewer than 35 subjects in the analysis population, with the same assumptions such as the null hypothesis as 50% and alternative hypothesis as 85%, the power and success criterion can be found in [Appendix 6.3, Table 13](#).

Supplementary Analyses for Group C

The following Supplementary analyses, but not limited to, will be conducted:

Analysis Population	Supplementary Analysis
TPVOE ^[1]	The analysis will be repeated using protocol sVOE instead of adjudicated sVOE.

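### As written, a pre-conditioning protocol or investigator VOE with no end date (or no end year) makes an event-free subject a non-responder in the supplementary VOE-CR and sVOE-CR analyses

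*SAP*

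**What the plan says.** **End dates.** One row of SAP 6.1 Table 11 covers start and end dates of VOEs and severe VOEs generally. For an end date it says "if year or the entire date is missing, set to DCO or end of study date, whichever occurs earlier". A missing day or month alone is filled in within the recorded year.

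**Exception.** The same row continues: "for adjudicated VOE, impute the missing entire VOE end date as below". Of the two branches that follow, the relevant one is "If adjudicated VOE start date is before conditioning start date, then the imputed date will be one day prior to the conditioning start date". Adjudicated events starting on or after conditioning still run to the data cut-off or end of study. No branch names protocol VOEs, investigator VOEs or protocol sVOEs.

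**Straddle rule.** SAP 4.4.1 counts a subject as a VOE-CR non-responder on this condition: "If a subject has an adjudicated VOE that occurs before 183 days but ends after 183 days after drug product infusion". SAP 4.4.2.1 has the same rule for sVOE-CR. Neither requires the event to start after infusion or consent.

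**Supplementary analyses.** SAP 4.4.1 repeats the primary analysis with protocol VOEs and, separately: "The primary analysis will be repeated using investigator VOE instead of adjudicated VOE". For sVOE-CR, SAP 4.4.2.1 says: "The analysis will be repeated using protocol sVOE instead of adjudicated sVOE".

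**Exposed records.** Protocol 6.2.5 collects all VOEs from the 24 months before consent and concedes: "It is recognized that retrospective collection of VOE information may be challenging". SAP Table 2 requires at least 4 protocol VOEs in that period for entry to the TPVOE.

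**The concern.** Three rules combine badly. The default end date has no link to when the event began, the pre-conditioning exception is limited to one event source, and the straddle rule has no lower bound on the start date. A crisis that began before consent and has no recorded end is treated as still in progress at Day 183, and the subject fails.

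The supplementary analyses show whether VOE-CR and sVOE-CR depend on adjudication. If open-ended old records are closed for the adjudicated source and left open for the others, part of any difference between the results reflects how completely pre-study end dates were recorded. A reader of the study report could take that as disagreement between the adjudication committee and the sites.

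**Working it through.** **1. The plan's own figures.** Inputs from SAP 3.1 and Table 13: n = 35, one-sided alpha 0.025, null and alternative 40% and 80% (VOE-CR), 50% and 85% (sVOE-CR). The criterion is the smallest r with P(X ≥ r | null) ≤ 0.025, X binomial.
- VOE-CR: r = 21, attained alpha 0.0133, power 0.998, lower 95% Clopper-Pearson limit 42.1%.
- sVOE-CR: r = 24, attained alpha 0.0205, power 0.996, lower limit 50.7%.

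Both match the plan (21 and 24 responders, power above 99%).

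**2. One record traced through the rules.** Assumed dates: event starts one year before consent, infusion about 5.5 months after consent, conditioning starts 6 days before infusion, study ends 730 days after infusion. The end date is missing and there is no event after infusion.
- Default rule: imputed end = 730 days after infusion. Start is before Day 183 and end is after it, so the subject is a **non-responder**.
- Adjudicated pre-conditioning branch, same record: imputed end = 7 days before infusion, so the subject is a **responder**.

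The score depends only on which branch is applied.

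**3. Size per affected subject.** A responder turned non-responder lowers the rate by 1/35 = 2.9 points.
- VOE-CR near the assumed rate: 28/35 (80.0%, lower limit 63.1%) becomes 27/35 (77.1%, lower limit 59.9%).
- VOE-CR at 21/35 (lower limit 42.1%, p = 0.013) becomes 20/35 (lower limit 39.4%, p = 0.030).
- sVOE-CR at 24/35 (lower limit 50.7%, p = 0.020) becomes 23/35 (lower limit 47.8%, p = 0.045).

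**4. Several affected subjects.** The number f is an assumption. The expected rate is (35 − f) × p / 35, with p the plan's alternative.
- VOE-CR, p = 0.80: f = 1 gives 77.7%, f = 5 gives 68.6%.
- sVOE-CR, p = 0.85: f = 1 gives 82.6%, f = 5 gives 72.9%.

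**5. Illustration by missingness rate, VOE-CR.** Let q be the chance that a baseline event lacks its end date or end year (assumed), independent across events, with m = 4 events, the TPVOE minimum. The reported rate is 0.80 × (1 − q)^4.
- q = 1%: 0.80 × 0.9606 = 76.8%.
- q = 2%: 0.80 × 0.9224 = 73.8%.
- q = 5%: 0.80 × 0.8145 = 65.2%.

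More baseline events per subject would enlarge the loss. Missing dates clustered within subjects or sites would shrink it at the same q.

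**The case against.** The best reply is about reading. The straddle rule also names only adjudicated events and reaches the other sources through the instruction to repeat the analysis with the event source swapped. If that swap carries the straddle rule over, it could carry Table 11's adjudicated branch over too, and the problem disappears. This is possible but not stated. Table 11 puts a general default next to a branch expressly limited to adjudicated VOEs, so a programmer following the text would apply the default. Where the SAP wants events that start before infusion and end after it left out, it says so: SAP 4.4.3.3 does this for annualized counts. VOE-CR and sVOE-CR have no such sentence.

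A second reply is that missing end dates may be rare. Inclusion Criterion 8 requires 24 months of care at centers with detailed records. Protocol pain and priapism events need medical-facility care, and protocol ACS needs oxygen or transfusion, so home-managed events can enter only the investigator-VOE repeat. The rule needs the year or whole date to be missing. All of this stands and limits the likely size.

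Stronger inferences are tempting but unsupported:
- *That the primary or key secondary result is distorted by open-ended baseline events.* Those analyses use adjudicated events, and the branch closes a pre-conditioning event whose whole end date is missing.
- *That the 21/35 or 24/35 criterion could be lost.* Those criteria belong to the adjudicated endpoints; the SAP sets none for the repeats. The boundary figures in step 3 show only sensitivity to one subject.
- *That running an adjudicated event from between conditioning and Day 182 to study end is an error.* It is an explicit, conservative choice, consistent with counting carry-over events as failures.

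**Conclusion.** Wrong as written, minor. On the literal text, a pre-conditioning protocol VOE, investigator VOE or protocol sVOE with no end date or end year turns a subject with no post-infusion event into a non-responder. This affects the supplementary VOE-CR analyses (protocol and investigator VOEs) and the supplementary sVOE-CR analysis (protocol sVOEs). The direction is against the product, and the practical risk is a spurious gap between adjudicated and unadjudicated results.

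The size is 2.9 points per affected subject at n = 35. The total effect is unknown because the documents give no count of such records; it is zero if there are none. The percentages in steps 4 and 5 rest on assumed counts or missingness rates, and those in step 5 also on independence. The conclusion also assumes that Table 11's limitation to adjudicated VOEs is meant as written.

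**What to change.** In SAP Table 11, extend the existing pre-conditioning branch, with imputed end equal to the day before conditioning starts, from adjudicated VOEs to protocol VOEs, investigator VOEs and protocol sVOEs. For these sources, word the trigger to match the default rule (year or entire date missing), so that a record lacking only its year is also closed.

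Leave the rule for events starting on or after conditioning unchanged. Sample size, power and success criteria stay as they are.

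The cost is one line of SAP text and a small programming change, using dates already collected and logic already specified for adjudicated events.

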- Change from baseline in markers of stress erythropoiesis, including erythropoietin and serum transferrin receptor

SCD Burden and Chronic Complications Assessments:

- Change from baseline in renal function as measured by eGFR

- Change from baseline in cardiac-pulmonary function via echocardiogram (tricuspid regurgitant jet velocity [TRJV], LVEF) and pulmonary function tests
- Change from baseline in meters walked during 6-minute walk test

Hospitalizations and Quality of Life:

- Change from baseline in annualized VOE-related hospital admissions and days
- Change from baseline in patient-reported quality of life, as measured by Patient Reported Outcomes Measurement Information System (PROMIS)

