4.4.3.5. Hospitalizations and Quality of Life

The final analysis will be based on subjects in the TP. If an interim analysis is performed for the hospitalization endpoint before the final analysis, the analysis will be based on the evaluable subjects defined in [Section 3.12](#); the quality of life endpoints will be presented based on all data available as of the data cut-off.

- **Change from baseline in annualized hospital admissions and days**

The number of VOE-related hospital admissions and in-patient VOE-related hospitalization days from post-drug product infusion discharge through last follow-up will be annualized and compared to the corresponding annualized values during the 2 years prior to Informed Consent. All hospitalizations for 3 groups will also be included data listings. The imputation rules for partial date of admission and discharge can be found in [Appendix 6.1, Table 11](#).

- **Change from baseline in patient-reported quality of life, as measured by PROMIS**

PROMIS-57 is used for subjects ≥18 years old and has 7 domains + 1 pain intensity question. PROMIS-49 (PROMIS Pediatric Profile 49 or PROMIS Parent Proxy Profile 49) is used for subjects <18 years old (from Group C only) and has 6 domains + 1 pain intensity question. Each domain has 8 questions. Standardized score ("T score") will be derived per the raw values from the answers to the questions and corresponding T score reference table.

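### For hospital stays with a missing day, SAP Table 11 imputes a duration that depends on whether the stay crosses a month end, not on how long it lasted

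*SAP*

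**What the plan says.** The endpoint is listed among the additional secondary efficacy endpoints (SAP 1.2.6.3): "Change from baseline in annualized VOE-related hospital admissions and days". SAP 4.4.3.5 says that "in-patient VOE-related hospitalization days from post-drug product infusion discharge through last follow-up will be annualized". The comparator is the same quantity over two years before consent: "annualized and compared to the corresponding annualized values during the 2 years prior to Informed Consent". For incomplete dates it points to Table 11: "The imputation rules for partial date of admission and discharge can be found in" Appendix 6.1.

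The Table 11 row on hospital or ER dates has these branches when a day is missing:

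- Discharge in a later month, discharge day missing: "and day of discharge is missing, then set as 01 for the missing day".
- Discharge in a later month, both days missing: "both day of discharge and admission are missing, then set as 01 for the missing day".
- Same month: "If the month of discharge is the same the month of admission, then duration of hospital = 1".

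A separate line covers the more incomplete case: "If both Month and Day are missing in either date, no imputation for duration of hospital".

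**The concern.** An imputed length of stay should reflect what is known about the stay. Here it is fixed mostly by where the stay falls relative to a month end. The same-month branch returns a constant and discards a known admission or discharge day. The both-missing branch returns the length of the admission month. The discharge-day branch always takes the minimum. A month-crossing stay with only the admission day missing has no rule, so the programmer would have to invent one.

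The row also fits poorly with another row of the same table. For a VOE end date with the day missing, Table 11 uses the last day of the month. Take a subject admitted with a VOE on 3 March whose VOE end day and discharge day are both unknown, but in March. The VOE runs to 31 March and the hospital stay lasts 1 day.

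At stake is the before/after comparison of hospital days. SAP 4.4.3.5 asks for no count of imputed stays and no sensitivity analysis, so a summary table would not show how far the rule had shaped it.

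**Working it through.** The 1-day figure is an assigned constant, so there is no calculation in the plan to reproduce. The check applies the rule to calendar dates.

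**Inputs.** The branches are those of Table 11. Duration is taken as discharge date minus admission date; the SAP does not define it, and counting both end days would add 1 to the imputed month-crossing values only. True length of stay is not given anywhere, so it is an assumption: L = 3, 5, 7 and 10 days, with admission equally likely on each of the 1,461 days of a four-year cycle.

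**Single stays.**

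| Stay | True days | Both days missing | Discharge day missing |
|---|---|---|---|
| 10 to 15 January | 5 | 1 | 1 |
| 2 to 30 January | 28 | 1 | 1 |
| 31 January to 1 February | 1 | 31 | 1 |
| 29 January to 3 February | 5 | 31 | 3 |
| 29 January to 28 February | 30 | 31 | 3 |

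With both days missing, a 28-day stay scores 1 and a 1-day stay scores 31.

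**Averages over the calendar.** With a mean month of 30.44 days (SAP 3.2 uses 30.4375), the chance that a stay crosses a month end is p = L / 30.44. For L = 5, p = 5 / 30.44 = 0.164.

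- Discharge day missing: a crossing stay is scored evenly over 1 to L, so the mean is (1 − p) × 1 + p × (L + 1)/2. For L = 5: 0.836 + 0.164 × 3 = 1.33. The understatement is (5 − 1.33)/5 = 73%.
- Both days missing: the mean is (1 − p) × 1 + p × 30.44. For L = 5: 0.836 + 0.164 × 30.44 = 5.83 (5.84 by enumeration).

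Full enumeration gives:

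| True stay | Crosses month end | Discharge day missing: mean | Understated by | Both missing: mean | Both missing: SD |
|---|---|---|---|---|---|
| 3 | 9.9% | 1.10 | 63% | 3.90 | 8.78 |
| 5 | 16.4% | 1.33 | 73% | 5.84 | 10.91 |
| 7 | 23.0% | 1.69 | 76% | 7.77 | 12.39 |
| 10 | 32.9% | 2.48 | 75% | 10.67 | 13.83 |

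A missing discharge day therefore gives a clear downward bias. Two missing days give an average 0.7 to 0.9 day too high (10.67 − 10 to 3.90 − 3) with a very large spread: a 5-day stay scores 1 in about 84% of cases and 28 to 31 in about 16%.

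**Effect on the endpoint.** One true 5-day baseline stay contributes 5/2 = 2.5 days per year. The rule can make that 1/2 = 0.5 or 31/2 = 15.5. The larger error is 13 days per year for that subject. Spread over the 36 treated Group C subjects in SAP Table 1, it moves the mean by 13/36 = 0.36 days per year; over all 45 treated subjects (7 + 1 + 1 + 36), by 13/45 = 0.29.

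**The case against.** The best reply is that this may hardly ever apply. Fully dated stays are untouched. Inclusion criterion 8 requires 24 months of care at centers with detailed records, Protocol 6.2.2 collects hospital visits linked to SCD complications, and the adjudication committee reviews source documents, including for events before enrollment. In-patient dates are among the items such records are most likely to hold. The number of partial dates could be zero. The row also covers ER visits, for which 1 day is a reasonable default. That all stands, and it limits the size of the problem. It does not make the rule right for in-patient stays when it is used.

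Four stronger readings are tempting and are not supported:

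- *Every same-month stay is set to 1 day.* The branch applies only when a day is missing.
- *Stays of about 30 days would dominate the mean.* One such stay moves a 36-subject mean by 0.36 days per year. SAP 3.2 also calls for medians, minima and maxima, and hospitalizations are listed, so a 31-day value would be visible.
- *Partial dates are common at baseline, usually with the discharge day unknown.* Protocol 6.2.5 says that retrospective collection of VOE information may be difficult, but it speaks of VOEs in general, including home-managed ones. No pattern or frequency is given.
- *The rule flatters the product.* If partial dates do cluster at baseline with the discharge day missing, baseline days are too low and the reduction after treatment is understated.

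Changing the rule is also not free. SAP 5.2 shows that analyses were already run for an interim CSR in this open-label study, so a change needs to be documented.

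**Conclusion.** The point holds for stays with a missing day, and it is minor. Followed as written, Table 11 gives durations that track the calendar rather than the stay, throws away known days, and leaves one pattern without a rule. For assumed stays of 3 to 10 days, the discharge-day-missing case understates length by about 63% to 76%. The both-missing case is close to unbiased on average and very noisy for each stay.

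The effect stops at annualized VOE-related hospital days, a secondary endpoint that Protocol 7.4.4.3 summarizes descriptively. VOE-CR, sVOE-CR and Globin Response do not use this duration, and the admissions half of the same endpoint does not use length of stay. The total effect cannot be computed because the number of partial dates is not given. Its net direction depends on how those dates split between baseline and follow-up. The percentages rest on the assumed stay lengths, admissions spread evenly over the calendar, and a literal reading of the row.

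**What to change.** Rewrite the Table 11 row for in-patient stays:

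1. When a day is missing, keep any day that is known.
2. Impute the length of stay as the subject's own median over fully dated VOE admissions in the same period (baseline or post-infusion). If there are none, use the median of the subject's own group, or of the whole Transplant Population where the group is too small. The endpoint is analyzed in the TP, so a Group C median alone would not suit Groups A and B.
3. Constrain the result to the known dates and months.
4. Apply the same rule when only the admission day is missing.
5. Report the number of imputed stays by period, and add a sensitivity summary using the shortest and longest stays the dates allow.

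There is a precedent in the same table: for some missing transfusion volumes it substitutes the subject's own mean. The cost is a few lines of text, minor programming, and a documented change from the interim CSR rule, with interim figures re-run if any imputed stays exist. If there are none, a statement to that effect is enough for the results already reported.
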